6.2.3 Rescue medication

There is no established, approved immunosuppressive treatment for SjS or MCTD, however, in case of acute, severe systemic manifestations, high dose steroid or other systemic immunosuppressant may be administered as rescue. Participants may receive nonsteroidal anti-inflammatory drugs (NSAIDs), paracetamol, or symptomatic care at the discretion of the treating physician as outlined in Section 6.2.1. Each concomitant drug must be individually assessed against all exclusion criteria and prohibited medication (Table 6-3). When in doubt the investigator should contact the Novartis medical monitor before randomizing a participant or allowing a new medication to be started. If any of the medications listed in Table 6-3 is deemed a necessary rescue therapy, the investigator must follow the actions to be taken outlined in this table. Any potential rescue medication is to be provided by the study center or personal physician. Participants should be encouraged to come for the remaining visits and end-of-study visit even when discontinued permanently from study medication.

Commercially Confidential Information

6.2.4 Restriction for study participants

For the duration of the study, participants should be informed and reminded of the restrictions outlined in this section.

6.2.4.1 Dietary restrictions and smoking

Study participants should not eat or drink for 90 minutes before the assessment of salivary flow. It is recommended that participants do not smoke for 90 minutes before the pre-dose PK assessment and until all the PK study assessments are performed on the study visits of Day 29 (Week 4), Day 85 (Week 12) and Day 169 (Week 24). Study participants should not eat grapefruit or drink grapefruit juice on Day 29 (Week 4), Day 85 (Week 12) and Day 169 (Week 24). Day 85 (Week 12) and Day 169 (Week 24) due to potential interference with PK assessments. It is also recommended that participants avoid ingestion of cruciferous vegetables (e.g. broccoli, brussel sprouts, cabbage, cauliflower) on these days.

6.2.4.2 Other restrictions

On the study days when PK assessments are performed, any permitted concomitant medication (see Section 6.2.1.1 and Section 6.2.1) should be separated by at least 3 hours of study drug intake. Moreover, on the study days when PK assessments are performed, participants have to avoid strenuous movements for 4 hours after dosing.

6.3 Preparation and dispensation

Each study site will be supplied with study drug in packaging as described under investigational and control drugs section.

A unique medication number is printed on the study medication label.

Investigator staff will identify the study medication kits to dispense to the participant by contacting the IRT and obtaining the medication number(s). The study medication has a 2-part label (base plus tear-off label), immediately before dispensing the medication kit to the participant, site personnel will detach the outer part of the label from the packaging and affix it to the source document.

6.3.1 Handling of study treatment and other treatment

6.3.1.1 Handling of study treatment

Study treatment must be received by a designated person at the study site, handled and stored safely and properly and kept in a secured location to which only the Investigator and designated site personnel have access. Upon receipt, all study treatment must be stored according to the instructions specified on the labels.

Clinical supplies are to be dispensed only in accordance with the protocol. Technical complaints are to be reported to the respective Novartis Country Organization (CO) Quality Assurance.

Medication labels will be in the local language and comply with the legal requirements of each country. They will include storage conditions for the study treatment but no information about the participant except for the medication number.

The investigator must maintain an accurate record of the shipment and dispensing of study treatment in a drug accountability log. Monitoring of drug accountability will be performed by field monitors during site or remote monitoring visits, and at the completion of the trial.

If study treatment is administered at home, participants will be asked to return all used and unused study treatment and packaging at every study visit and the end of the study or at the time of discontinuation of study treatment.

Confidential

The site may destroy and document destruction of unused study treatment, drug labels and packaging as appropriate in compliance with site processes, monitoring processes, and per local regulation/guidelines. Otherwise, the investigator will return all unused study treatment, packaging, drug labels, and a copy of the completed drug accountability log to the Novartis monitor or to the Novartis address provided in the investigator folder at each site.

6.3.1.2 Handling of other treatment

Not applicable.

6.3.2 Instructions for prescribing and taking study treatment

Table 6-4 Dose and treatment schedule

Investigational / Control Drug (Name and Strength)	Dose	Frequency and/or Regimen
MHV370 100 mg	200 mg (2 capsules x 100 mg)	b.i.d. (twice daily)
Placebo	2 matching placebo capsules	b.i.d. (twice daily)

All kits of study treatment assigned by the IRT will be recorded in the IRT system.

- Participants should be instructed to take MHV370 twice daily at approximately the same time each day, around 12 hours apart.
- Participants should be instructed not to make up missed doses, i.e. when the full dose is not taken within 4 hours after the time of the usual dosing.
- The first dose of MHV370 should be taken in the morning of Day 1 and the last dose of MHV370 should be taken in the morning of Day 169.
- On study visits, the participant should take their morning dose of MHV370 at the clinic.
- Participants should take MHV370 without regard to food. Each dose may be taken with a glass of water.
- Participants should be instructed to swallow whole capsules and not to chew or open them.
- If vomiting occurs during the course of treatment, participants should not take the study treatment MHV370 again before the next scheduled dose.
- Participants will be provided with individual diaries to record each administration of study treatment. These will be checked regularly by site staff.

6.4 **Participant numbering, treatment assignment, randomization**

6.4.1 Participant numbering

Each participant is identified in the study by a Participant Number (Participant No.), that is assigned when the participant is enrolled for screening and is retained for the participant throughout his/her participation in the trial. A new Participant No. will be assigned at the subsequent enrollment if the participant is re-screened. The Participant No. consists of the Center Number (Center No.) (as assigned by Novartis to the investigative site) with a sequential participant number suffixed to it, so that each participant's participation is numbered uniquely across the entire database. Upon signing the informed consent form, the participant is assigned to the next sequential Participant No. available.

A new ICF will need to be signed if the investigator chooses to re-screen the participant after a participant has screen failed.

6.4.2 Treatment assignment, randomization

At Day 1, all eligible participants will be randomized via IRT to one of the treatment arms. The investigator or his/her delegate will contact the IRT after confirming that the participant fulfills all the inclusion/exclusion criteria. The IRT will assign a randomization number to the participant, which will be used to link the participant to a treatment arm and will specify a unique medication number for the first package of study treatment to be dispensed to the participant.

The randomization numbers will be generated using the following procedure to ensure that treatment assignment is unbiased and concealed from participants and investigator staff. A participant randomization list will be produced by the IRT provider using a validated system that automates the random assignment of participant numbers to randomization numbers. These randomization numbers are linked to the different treatment arms, which in turn are linked to medication numbers. A separate medication list will be produced by or under the responsibility of Novartis Global Clinical Supply (GCS) using a validated system that automates the random assignment of packs containing the study treatment.

Commercially Confidential Information

The randomization scheme for participants will be reviewed and approved by a member of the Randomization Office.

6.4.2.1 Replacement policy

Participants will not be replaced on this study.

6.5 Treatment blinding

Participants, investigator staff and the persons performing the assessments will remain blinded to the study treatment from the time of randomization until database lock, except where indicated below.

Site staff

All site staff (including study investigator and study nurse) will be blinded to study treatment throughout the study.

Unblinding a single participant at site for safety reasons (necessary for participant management) will occur via an emergency system in place at the site. As a result, the participant should be discontinued from the study treatment.

Sponsor staff

The following unblinded sponsor roles are required for this study:

- Unblinded clinical staff managing drug re-supply to site
- Unblinded sample analysts (PK)

The following methods will be used to maintain the blind:

- 1. all unblinded personnel will keep randomization list and data or information that could unblind other study team members confidential and secure except as described below
- 2. the identity of the treatments will be concealed by the use of study drug that are all identical in packaging, labeling, schedule of administration and appearance.

Sponsor clinical staff are required to assist in the management and re-supply of investigational drug product. These individuals are not provided with randomization lists directly, but may be unblinded through communication of drug re-supply needs.

The sample analysts will receive a copy of the randomization schedule (via request to the Randomization Office), to facilitate analysis of the samples. The sample analysts will provide the sample data to the study team under blinded conditions unless otherwise allowed.

The study statistician will be able to access the randomization list for interim analyses and is allowed to share unblinded information with the rest of the clinical team as appropriate for internal decision purposes. For example, unblinded summaries and unblinded individual data can be shared with the team for interim analyses.

Study programmers and other personnel involved in study data analysis (e.g. biomarker expert) are allowed to access treatment assignment information for the purpose of conducting interim analyses.

The clinical trial team is allowed to share unblinded results with other sponsor staff (e.g. decision boards) as required for internal decision making on the study or the project at the time of interim analyses while the study is ongoing.

Following final database lock all roles may be considered unblinded.

Table 6-5Blinding and unblinding plan

Commercially Confidential Information

6.6 Dose escalation and dose modification

Investigational treatment dose adjustments and/or interruptions are not permitted, with the exception of interruption in case of confirmed SARS-CoV2 infection, as described under Section 4.5.

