10.2 Additional Safety Monitoring

10.2.1 Liver safety monitoring

To ensure participant safety and enhance reliability in determining the hepatotoxic potential of an investigational drug, a standardized process for identification, monitoring and evaluation of liver events has to be followed.

Please refer to Section 16.2 for complete definitions of liver laboratory triggers.

Once a participant is exposed to study treatment, every liver event defined in Table 16-1 should be followed up by the investigator or designated personnel at the trial site, as summarized below. Additional details on actions required in case of liver events are outlined in Section 16.2.

- Repeat liver chemistry tests (i.e. ALT, AST, TBL, PT/INR, ALP and G-GT) to confirm elevation. These liver chemistry repeats will be performed using the central laboratory. If results will not be available from the central laboratory, then the repeats can also be performed at a local laboratory to monitor the safety of the participant. If a liver event is subsequently reported, any local liver chemistry tests previously conducted that are associated with this event should have results recorded on the appropriate CRF.
- If the initial elevation is confirmed, close observation of the participant will be initiated, including consideration of treatment interruption if deemed appropriate.
- Discontinuation of the investigational drug (refer to the Discontinuation of study treatment, Section 9.1.1), if appropriate
- Hospitalization of the participant if appropriate

- Causality assessment of the liver event
- Thorough follow-up of the liver event. These investigations can include based on investigator's discretion: serology tests, imaging and pathology assessments, hepatologist's consultancy.
- Obtaining a more detailed history of symptoms and prior or concurrent diseases.
- Obtaining a history of concomitant drug use (including nonprescription medications and herbal and dietary supplement preparations), alcohol use, recreational drug use, and special diets.
- Exclusion of underlying liver disease
- Imaging such as abdominal US, CT or MRI, as appropriate
- Obtaining a history of exposure to environmental chemical agents.
- Considering gastroenterology or hepatology consultations.

All follow-up information and procedures performed must be recorded as appropriate in the eCRF.

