16.2 Appendix 2: Liver event and laboratory trigger definitions & follow-up requirements

Confidential

	Definition/ threshold
Liver laboratory triggers	 ALT or AST > 5 × ULN
If ALT, AST and total bilirubin normal at baseline:	 ALP > 2 × ULN (in the absence of known bone pathology)
	 Total bilirubin > 3 × ULN (in the absence of known Gilbert syndrome)
	 ALT or AST > 3 × ULN and INR > 1.5
	 Potential Hy's Law cases (defined as ALT or AST > 3 × ULN and Total bilirubin > 2 × ULN [mainly conjugated fraction] without notable increase in ALP to > 2 × ULN)
	 Any clinical event of jaundice (or equivalent term)
	 ALT or AST > 3 × ULN accompanied by (general) malaise, fatigue, abdominal pain, nausea, or vomiting, or rash with eosinophilia
	Any adverse event potentially indicative of a liver toxicity
If ALT or AST abnormal at baseline:	 ALT or AST > 3x baseline or > 300 U/L (whichever occurs first)

Table 16-1 Liver event and laboratory trigger definitions

Table 16-2	6-2 Follow up requirements for liver laboratory triggers - ALT, AST, TBL			
	ALT	TBL	Liver Symptoms	Action
ALT increase w	vithout bilirubin increa	se:		
	If normal at baseline: ALT > 3 x ULN If elevated at baseline: ALT > 2 x baseline or > 300 U/L (whichever occurs first)	Normal For participants with Gilbert's syndrome: No change in baseline TBL	None	 No change to study treatment Measure ALT, AST, ALP, GGT, TBIL, INR, albumin, CK, and GLDH in 48-72 hours. Follow-up for symptoms.
	If normal at baseline: ALT > 5 x ULN for more than two weeks If elevated at baseline: ALT > 3 x baseline or > 300 U/L (whichever occurs first) for more than two weeks	Normal For participants with Gilbert's syndrome: No change in baseline TBL	None	 Interrupt study drug Measure ALT, AST, ALP, GGT, TBIL, INR, albumin, CK, and GLDH in 48-72 hours.
	If normal at baseline: ALT > 8 x ULN	Normal	None	Follow-up for symptoms.Initiate close
ALT increase w	vith bilirubin increase:			monitoring and workup
	If normal at baseline: ALT > 3 x ULN If elevated at baseline: ALT > 2 x baseline or > 300 U/L (whichever occurs first)	TBL > 2 x ULN (or INR > 1.5) For participants with Gilbert's syndrome: Doubling of direct bilirubin	None	 for competing etiologies. Study drug can be restarted only if another etiology is identified and liver enzymes return to
	If normal at baseline: ALT > 3 x ULN If elevated at baseline:	Normal or elevated	Severe fatigue, nausea, vomiting, right upper quadrant pain	baseline.

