Table 16-2 Follow up requirements for liver laboratory triggers - ALT, AST, TBL

ALT	TBL	Liver Symptoms	Action
ALT > 2 baseline			
or > 300 (whiche occurs f	/er		

Table 16-3Follow up requirements for liver laboratory triggers - Isolated
Hyperbilirubinemia

Criteria	Actions required	Follow-up monitoring
Total Bilirubin (isolated)		
>1.5 – 3.0 ULN	 Maintain treatment Repeat LFTs within 48-72 hours 	Monitor LFTs weekly until resolution to ≤ Grade 1 or to baseline
> 3 - 10 × ULN (in the absence of known Gilbert syndrome)	 Interrupt treatment Repeat LFT within 48-72 hours Hospitalize if clinically appropriate 	Monitor LFTs weekly until resolution to ≤ Grade 1 or to baseline (ALT, AST, total bilirubin, Alb, PT/INR, ALP and GGT)
	 Establish causality Record the AE and contributing factors (e.g. conmeds, med hx, lab) in the appropriate CRF 	Test for hemolysis (e.g. reticulocytes, haptoglobin, unconjugated [indirect] bilirubin)
> 10 x ULN	 Discontinue the study treatment immediately Hospitalize the participant Establish causality Record the AE and contributing factors(e.g. conmeds, med hx, lab)in the appropriate CRF 	ALT, AST, total bilirubin, Alb, PT/INR, ALP and GGT until resolution (frequency at investigator discretion)
Any AE potentially indicative of a liver toxicity	 Consider study treatment interruption or discontinuation Hospitalization if clinically appropriate Establish causality Record the AE and contributing factors(e.g., conmeds, med hx, lab) in the appropriate CRF 	Investigator's discretion

Based on investigator's discretion investigation(s) for contributing factors for the liver event can include: Serology tests, imaging and pathology assessments, hepatologist's consultancy; obtaining more detailed history of symptoms and prior or concurrent diseases, history of concomitant drug use, exclusion of underlying liver disease.

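### Protocol 6.6 permits study-drug interruption only for confirmed SARS-CoV-2 infection, while Tables 16-2 and 16-3 direct interruption for defined liver findings; no visible text reconciles them.

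*Protocol*

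**What the plan says.** Protocol 6.6 is a single rule with a single exception: "dose adjustments and/or interruptions are not permitted, with the exception of interruption in case of confirmed SARS-CoV2 infection". The only section it cites is 4.5, for the SARS-CoV-2 exception. It does not mention liver events, Section 10.2.1 or Section 16.2.

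Protocol 16.2 contains two tables of follow-up actions.

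- Table 16-2 (ALT, AST, bilirubin). The first row, a lesser ALT rise, makes no change to treatment. From the row for "ALT > 5 x ULN for more than two weeks" (or its elevated-baseline equivalent), with normal bilirubin and no symptoms, the action is "Interrupt study drug". The same action cell adds "Study drug can be restarted only if another etiology is identified" and liver enzymes have returned to baseline.
- Table 16-3 (isolated hyperbilirubinemia). Under the column heading "Actions required", the row for total bilirubin above 3 and up to 10 x ULN, without known Gilbert syndrome, says "Interrupt treatment". The next row, above 10 x ULN, says "Discontinue the study treatment immediately".

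Sites are routed to these tables. Section 10.2.1 says "Additional details on actions required in case of liver events are outlined in Section 16.2". Section 9.1.1 also points to 16.2 when a liver event occurs, but about discontinuation, which that section defines as a permanent stop.

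For the primary analysis, Protocol 12.4.3 and SAP 2.5.3 treat the two kinds of stop differently. After a permanent discontinuation, all later data count as missing. For a temporary one, only data within the gap do. The SAP adds a threshold: more than two doses missed in a row.

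**The concern.** An investigator with a participant who meets a liver trigger needs one instruction about study drug. Here the dosing section forbids an interruption that the safety appendix directs. Following the tables departs from 6.6, and following 6.6 departs from the tables. That is a conduct and safety problem first, in a compound that Protocol Section 3 says is being given for the first time in these patients.

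There is a secondary statistical side. If sites resolve the conflict differently, the same finding could lead to a temporary stop with restart at one site, a permanent stop at another, and continued dosing at a third. Under the intercurrent-event rules these paths set different data to missing, so the post-event data kept for the primary endpoint could depend on which section a site happened to read.

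**Working it through.** No arithmetic applies; the point rests on comparing the text.

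1. **Scope of 6.6.** It covers dose adjustments and interruptions of the investigational treatment and names one exception, confirmed SARS-CoV-2 infection. It has no liver exception and no pointer to the liver sections.

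2. **Do the tables direct an interruption, or only suggest one?** They direct it. In both tables the wording is an instruction, and in Table 16-3 it stands under "Actions required". Where Table 16-3 wants only consideration, in its last row on adverse events that may indicate liver toxicity, it says so. The instruction is therefore deliberate.

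3. **Could interrupting here mean permanent discontinuation, which 6.6 would not bar?** No. Table 16-2 states when drug may be restarted. Table 16-3 gives interruption and "Discontinue the study treatment immediately" as actions for different bilirubin ranges. Both tables mean a temporary stop.

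4. **Does the cited Section 4.5 supply the missing exception?** Most of 4.5 is redacted, so its full text cannot be checked. But 6.6 cites it only for the SARS-CoV-2 exception, and nothing visible there concerns liver events.

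5. **Does other text reconcile the two?** Section 9.1.1 refers to 16.2 for discontinuation, not for temporary stops. Section 10.2.1 refers to 16.2 for actions in liver events. Neither mentions 6.6 or says that it yields. Section 14.1 allows immediate safety action but describes it as possibly a protocol deviation.

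6. **Limits of the extracted text.** Table 16-2 is broken, so how many rows its interruption cell spans is uncertain. The instruction and the first row it applies to are legible, and Table 16-3 shows the conflict without it.

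7. **Link to the analysis.** Take a participant with a liver trigger before Week 24.
   - Interrupted, restarted, and Week 24 after the restart: only visits in the gap are set to missing, and Week 24 is kept.
   - Stopped permanently: every later visit, including Week 24, is set to missing.
   - Interrupted and not restarted by Week 24: Week 24 is missing in either case, so at that visit the classification makes no difference.
   - Dosing continued: nothing is set to missing for this reason.

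   The rules work on what happened to the drug, so each path has a defined treatment. What 6.6 and the tables leave open is which path a site takes.

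**The case against.** The best reply is that a site is not really lost. Section 10.2.1 requires a standardized process for liver events and sends the site to 16.2. Section 9.1.1 points the same way. Section 14.1 expects the investigator to act at once for participant safety, even if that means a deviation. The adverse event section lists interruption of drug among possible responses. On this reading, 6.6 is a general dosing rule that lacks a cross-reference, and the specific liver instructions apply in practice.

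Much of this stands. The routing and the safety provision narrow the dilemma, and it would be wrong to say that sites have no guidance. But 6.6 lists its exceptions and stops at one, and no visible text says that a specific rule overrides it. Relying on 14.1 concedes the point, because it classes the action as a possible deviation from a protocol whose own appendix directs it.

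Two stronger readings are tempting and should be resisted. A reader might infer that 10.2.1, which asks that interruption be considered, is a further conflicting rule. It presents itself as a summary and refers to 16.2 for detail, where the graded rows range from no change to interruption; its wording fits over those rows. A reader might also treat the consider-type wording in 6.7.2 and 16.3 as a direct contradiction. Those passages offer discontinuation as well, so a site can satisfy them and 6.6 together. They do name an option that 6.6 excludes, but the direct conflict is between 6.6 and the two liver tables.

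**Conclusion.** The contradiction is on the face of the protocol. Section 6.6 allows one exception and none for liver events, and Tables 16-2 and 16-3 each direct a temporary stop outside that exception. As written, they cannot both be followed. This should be fixed because it concerns the handling of defined liver signals.

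The statistical consequence is real but limited. A reader might infer that the primary analysis is undefined or biased by this. The documents do not support that. Permanent and temporary stops each have a rule, participants who stop drug are asked to keep attending visits (Protocol Section 8), and for SjS a supplementary analysis keeps data after either kind of stop (Protocol 12.4.6). The documents give no frequency of liver events, and a participant without a Week 24 value still contributes earlier visits to the repeated-measures model, so a count of participants would not measure the effect on the estimate. Its size is unknown.

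Nor do the documents show that a participant interrupted under the liver tables would leave the PD analysis set. That set excludes deviations with relevant impact on efficacy data, but the contents of SAP Table 5-3 are not visible.

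The conclusion assumes that the redacted part of Section 4.5 contains no liver exception. The point takes no view on which clinical rule is right.

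**What to change.** Reconcile Section 6.6 with Tables 16-2 and 16-3 in a protocol amendment, so that a site reading either place finds the same instruction for the liver findings the tables define. Add cross-references in both directions between 6.6 and 16.2. Send sites a short clarification. The sponsor's medical team decides the clinical content; the statistical request is only that the passages agree.

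The cost is amendment wording and one site letter, with no added visits or procedures. SAP 2.5.3 already has a rule for both kinds of stop and needs no change on this account, unless the reconciled text brings in a kind of stop that it does not cover.
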